5.5.9.1.3. Vital Signs and Weight

Vital signs collected during the study include systolic and diastolic blood pressure (SBP/DBP), pulse, and temperature. Blood pressure and pulse measurements will be taken when the patient is in a sitting position. Three measurements of sitting blood pressure and pulse will be collected at approximately 30- to 60-second intervals at every visit and the 3 sitting blood pressure measurements and 3 pulse values will be averaged and used as the value for that visit.

[Table CGAL.5.4](#) displays the criteria used to define treatment emergent, potentially clinically significant changes and sustained elevation in vital signs and weight. The last column of the table displays the patient populations for each analysis based on baseline categories. The number and percent of patients meeting these criteria will be summarized. Treatment group comparisons will be performed using Fisher’s exact test for SP III.

The criteria to identify patients with treatment-emergent abnormal changes generally consist of 2 parts: an absolute threshold and a change from baseline amount.

- The absolute threshold in the criteria is based on 1) minimum postbaseline when the direction is low and 2) maximum postbaseline when the direction is high.
- The change from baseline amount in the criteria is 1) decrease from baseline (defined below and in [Table CGAL.5.2](#)) to minimum postbaseline when the direction is low; 2) increase from baseline (defined below and in [Table CGAL.5.2](#)) to maximum postbaseline when the direction is high.

The baseline for SBP, DBP, and pulse is defined as the last nonmissing value during the baseline period (See [Table CGAL.5.2](#)). To be exact,

- The baseline for SBP, DBP, and pulse is defined as the last nonmissing value before randomization. The rationale for using the last available value in the baseline period is to minimize the potential confound of discontinuing or dose stabilization of medications that modulate BP and pulse during the screening phase (which is early in the baseline period).

This baseline definition for SBP, DBP, and pulse applies to all analyses (both continuous and categorical).

The baseline and postbaseline values for temperature and weight are defined below (also in [Table CGAL.5.2](#)):

- For continuous analyses of temperature and weight, last nonmissing baseline during the baseline period will be used as the baseline value.
- For the analyses of categorical changes of interest in temperature and weight:
 - The baseline is defined as the minimum value during baseline period when the direction is low.
 - The baseline is defined as the maximum value during the baseline period when the direction is high.

Table CGAL.5.4. Criteria for Treatment-Emergent, Potentially Clinical Significant and Categorical Changes and Sustained Elevation in Vital Signs and Weight

Parameter	Direction	Criteria	Patients Population Defined by Baseline Categories
Systolic BP (mm Hg) (sitting)	Low	≤ 90 and decrease ≥ 20	>90 ; ≤ 90 ; All patients
	High	≥ 140 and increase ≥ 20	<140 ; ≥ 140 ; All patients
	PCS High	≥ 180 and increase ≥ 20	<180 ; ≥ 180 ; All patients
	Sustained Elevation	≥ 140 and increase ≥ 20 at 2 consecutive visits	<140 ; ≥ 140 ; All patients
Diastolic BP (mm Hg) (sitting)	Low	≤ 50 and decrease ≥ 10	>50 ; ≤ 50 ; All patients
	High	≥ 90 and increase ≥ 10	<90 ; ≥ 90 ; All patients
	PCS High	≥ 105 and increase ≥ 15	<105 ; ≥ 105 ; All patients
	Sustained Elevation	≥ 90 and increase ≥ 10 at 2 consecutive visits	<90 ; ≥ 90 ; All patients
Systolic BP or Diastolic BP (mm Hg) (sitting)	Sustained Elevation	Meeting criteria for systolic BP for 2 consecutive visits or meeting criteria for diastolic BP for 2 consecutive visits or both	All patients
Pulse (bpm) (sitting)	Low	<50 and decrease ≥ 15	≥ 50 ; <50 ; All patients
	High	>100 and increase ≥ 15	≤ 100 ; >100 ; All patients
	Sustained Elevation	>100 and increase ≥ 15 at 2 consecutive visits	≤ 100 ; >100 ; All patients
Weight (kg)	Low	(Loss) decrease $\geq 7\%$	All patients
	High	(Gain) increase $\geq 7\%$	All patients

Criteria for Treatment-Emergent, Potentially Clinical Significant and Categorical Changes and Sustained Elevation in Vital Signs and Weight

Parameter	Direction	Criteria	Patients Population Defined by Baseline Categories
Temperature (° F)	Low	<96° F and decrease $\geq 2^{\circ}$ F	$\geq 96^{\circ}$ F
	High	$\geq 101^{\circ}$ F and increase $\geq 2^{\circ}$ F	<101° F

Abbreviations: BP = blood pressure; PCS= Potentially Clinically Significant; mm Hg = millimeters of mercury; bpm = beats per minute; kg = kilograms; ° F = degrees Fahrenheit.

5.5.9.1.4. *Electrocardiogram Intervals and Heart Rate*

Analyses of corrected QT (QTc) interval and QTcF (msec) will be calculated with Fridericia's formula as $QT/RR^{1/3}$. For the QTc calculations, the unit for QT is milliseconds and the unit for RR is seconds. For patients with QRS ≥ 120 milliseconds at any time during the study, the QT and QTc interval will be excluded from the analyses. A listing of ECG data for patients with QRS ≥ 120 milliseconds at any time during the study will be provided.

The baseline for ECG is defined as the last nonmissing baseline value during the baseline period. To be exact,

- The baseline for ECG is defined as the last nonmissing value before randomization. The rationale for using the last available value in the baseline period is to minimize the potential confound of discontinuing or dose stabilization of medications that modulate ECG during the screening phase (which is early in the baseline period).

This baseline definition for ECG applies to all analyses (both continuous and categorical, quantitative and qualitative).

The baseline and postbaseline values are summarized in [Table CGAL.5.2](#).

The number and percent of patients meeting criteria for treatment-emergent abnormalities in ECG intervals (PR, QRS, and QTcF) and heart rate at any time during study will be summarized. Treatment group comparisons will be performed using Fisher's exact test for SP III.

[Table CGAL.5.5](#) displays the criteria for treatment-emergent changes in ECG intervals and heart rate.

- For treatment emergent low analyses: Patients with normal or high values at baseline (no low values) will be included.
- For treatment emergent high analyses: Patients with normal or low values at baseline (no high values) will be included.
- For treatment emergent increase analyses: Patients with a baseline and at least 1 postbaseline result will be included.

Table CGAL.5.5. Criteria for Treatment-Emergent Changes in ECG Intervals and Heart Rate

Parameter	Direction	Criteria	
Heart Rate (bpm)	Low	<50 and decrease ≥ 15	
	High	>100 and increase ≥ 15	
PR Interval (msec)	Low	<120	
	High	≥ 220	
QRS Interval (msec)	Low	<60	
	High	≥ 120	
QTcF (msec)	Low	Males: <330	Females: <340
	High	Males: >450	Females: >470
	PCS High	>500 msec	
	Increase	Increase >30 msec	
		Increase >60 msec	
		Increase >75 msec	

Abbreviations: bpm = beats per minute; ECG = electrocardiogram; PCS = Potentially Clinically Significant; QTcF = Fridericia's corrected QT interval.

In addition, qualitative ECG abnormalities will be evaluated that will include summaries of 11 ECG categories (Axis, Rhythm, Conduction, Ischemia, Infarction, Injury, Morphology, U-waves, T-waves, ST Segment, and Other Abnormalities) of qualitative findings at any time postbaseline. A category is a collection of possible descriptions (findings) of 1 qualitative aspect of an ECG. A category name is the name of the qualitative aspect of the ECG (for example, Rhythm, Conduction, Morphology, Ischemia, and so forth). A finding is 1 of the possible specific descriptions (for example, Sinus Bradycardia, Acute Septal Infarction) within a category.

A shift table summary of qualitative ECGs at any time will be produced, to assess shifts from baseline normal to postbaseline abnormal for the overall ECG and for each of the 11 finding categories mentioned above.

The summaries of the 11 ECG categories will exclude ECGs with any of the following: overall ECG could not be evaluated by the cardiologist, lead reversals or <9 leads, nonmatching demographic data, and those suggesting patient identification errors.

5.5.9.1.5. *Laboratory Tests*

The incidence rates of patients with treatment-emergent abnormal, high, or low laboratory values for each laboratory test based on Covance reference ranges at any time postbaseline will be summarized. The baseline and postbaseline definitions are summarized in [Table CGAL.5.2](#). The treatment comparisons will be assessed using Fisher's exact tests for SP III.

Patients will be defined as having a treatment-emergent low value if they have all normal or high values at baseline, followed by a value below the lower reference limit at any postbaseline visit. Patients with all normal or high values at baseline (no low values) will be included in the analysis of treatment-emergent low laboratory values. Patients will be defined as having a treatment-emergent high value if they have all normal or low values at baseline, followed by a value above the upper reference limit at any postbaseline visit. Patients with all normal or low values at baseline (no high values) will be included in the analysis of treatment-emergent high laboratory values.

For analytes simply classified as normal or abnormal, patients will be defined as having a treatment-emergent abnormal value if they have all normal values at baseline, followed by an abnormal value at any postbaseline visit. Patients with all normal values at baseline will be included in the analysis of treatment-emergent abnormal laboratory values.

The incidence of patients with the following elevations in hepatic laboratory tests at any time postbaseline will also be summarized and comparison between treatment groups for SP III using Fisher's exact test.

- The percentages of patients with an alanine aminotransferase (ALT) or aspartate aminotransferase (AST) measurement greater than or equal to 3 times (3 \times), 5 times (5 \times), and 10 times (10 \times) the Covance upper limit of normal (ULN) during the treatment period will be summarized for all patients with a postbaseline value.

- The percentages of patients with an alkaline phosphatase (ALP) greater than or equal to 2 times ($2\times$) the Covance ULN during the treatment period will be summarized for all patients with a postbaseline value.
- The percentages of patients with a total bilirubin (TBIL) measurement greater than or equal to 2 times ($2\times$) ULN during the treatment period will be summarized for all patients with a postbaseline value.

The analysis of elevation in ALT, AST, ALP, and TBIL will contain 3 subsets:

- patients whose nonmissing maximum baseline value is less than or equal to $1\times$ ULN for ALT, AST, ALP, and TBIL.
- patients whose nonmissing maximum baseline value is greater than $1\times$ ULN for ALT, AST, ALP, and TBIL, and at the same time less than or equal to $2\times$ ULN for ALT and AST, $1.5\times$ ULN for ALP and TBIL.
- patients whose nonmissing maximum baseline value is greater than $2\times$ ULN for ALT and AST, $1.5\times$ ULN for ALP and TBIL.

A listing of patients who had met any following criteria postbaseline will be provided over all study phases: $ALT \geq 3 \times$ ULN, or $AST \geq 3 \times$ ULN, or $ALP \geq 2 \times$ ULN, or $TBIL \geq 2 \times$ ULN.

5.5.9.1.6. *Immunogenicity*

In the immunogenicity assay process, each sample is potentially examined multiple times, according to a hierarchical procedure, to produce a sample ADA assay result and potentially a sample NAb assay result. The cut points used, the drug tolerance of an assay, and the possible values of titers are operating characteristics of the assay.

It can be the case that the presence of high concentrations of galcanezumab will affect the measurements of the presence of ADA or NAb, and conversely high levels of ADA or NAb may affect the measurement of galcanezumab concentration. Thus, a GMB drug concentration, assessed from a sample drawn at the same time as the ADA sample, plays a key role in clinical interpretation of a sample when the laboratory result is Not Detected.

5.5.9.1.6.1. Definitions of Sample Anti-drug Antibody Status

Table CGAL.5.6 and Table CGAL.5.7 list sample ADA assay results and clinical interpretation of the sample results.

Table CGAL.5.6. Sample ADA Assay Results

Sample Laboratory Result	Explanation
Detected	ADA are detected and confirmed.
Not Detected	The raw result as reported from the laboratory indicates not detected. The clinical interpretation of such results depends on other factors (see below).
No Test, QNS, etc.	Sample exists but was unevaluable by the assay

Abbreviation: ADA = anti-drug antibody.

Table CGAL.5.7. Sample Clinical ADA Interpretation Results

Sample Laboratory Result	Explanation
ADA Present	ADA assay result detected.
ADA Not Present	ADA assay result is Not Detected and simultaneous drug concentration is at a level that has been demonstrated to not interfere in the ADA detection method (i.e., drug concentration is below the assay's drug tolerance level). For patients receiving placebo, drug concentration is not assessed and is assumed to be below the assay's drug tolerance level.
ADA Inconclusive	ADA assay result is Not Detected but drug concentration in the sample is at a level that can cause interference in the ADA detection method.
ADA Not Detected with Drug Concentration Not Available	If drug concentration analysis was planned but result is not available for a treatment-period sample, a Not Detected sample will be declared ADA Not Detected with Drug Concentration Not Available. In the computation of Patient ADA status (see below, Section 5.5.9.1.6.2), these samples will be considered ADA Not Present, on the basis of prior knowledge that the drug tolerance level of the ADA assay is high relative to the expected drug concentration levels.
ADA Missing	ADA sample not drawn, QNS, not tested, etc., causing there to be no laboratory result reported or the result is reported as "no test".

Abbreviation: ADA = anti-drug antibody.

Parallel terminology applies for NAb Detected, NAb Not Detected, NAb Present, NAb Not Present, NAb Inconclusive, NAb Not Detected with Drug Concentration Not Available, and NAb Missing. Anti-drug antibody and NAb are distinct assays and have different assay-operating characteristics.

5.5.9.1.6.2. Definitions of Patient Anti-drug Antibody Status

Patient evaluable for TE ADA: A patient is evaluable for TE ADA if the patient has a nonmissing baseline ADA result and at least 1 nonmissing postbaseline.

TE ADA positive (TE ADA+) patient: A patient who is evaluable for TE ADA is TE ADA+ if either of the following holds:

- **Treatment-induced:** The patient has baseline status of ADA Not Present and at least one postbaseline status of ADA Present with titer ≥ 20 (ie, 2^*MRD where for this ADA assay the MRD, the minimum required dilution of the ADA assay, is 10).
- **Treatment-boosted:** The patient has baseline and postbaseline status of ADA Present, with the postbaseline titer being 2 dilutions (4-fold) greater than the baseline titer. That is, the patient has baseline status of ADA Present, with titer 1:B, and at least 1 postbaseline status of ADA Present, with titer 1:P, with $\text{P/B} \geq 4$.

TE ADA Inconclusive patient: A patient who is evaluable for TE ADA is TE ADA Inconclusive if $\geq 20\%$ of the patient's postbaseline samples, drawn predose, are ADA Inconclusive and the patient is not otherwise TE ADA+.

TE ADA negative (TE ADA-) patient: A patient who is evaluable for TE ADA is TE ADA- when the patient is not TE ADA+ and the patient is not TE ADA Inconclusive.

5.5.9.1.6.3. Analyses to Be Performed

To evaluate the changes in immunogenicity data (Anti-galcanezumab [ADA and NAb]) after treatment, the number and proportion of patients who are TE ADA+ will be tabulated where proportions are relative to the number of patients who are TE ADA evaluable as defined in Section 5.5.9.1.6.2). The baseline and postbaseline definitions for each analysis period is shown in Table CGAL.5.2. In detail the following statistical analyses for each immunogenicity analyte (ADA and NAb) are planned:

- the incidence of TE ADA will be summarized as follows:
 - for safety population during double-blind treatment phase and compared between treatment arms using Fisher's exact test
 - for the ADA follow-up cohort during double-blind treatment phase, the ADA follow-up cohort is defined as patients in the safety population with ADA assessment during post-treatment phase
 - for the ADA follow-up cohort during double-blind treatment phase and post-treatment phase
- shift from baseline to maximum postbaseline ADA titers for the galcanezumab-treated patients during double-blind treatment phase
- summary of time to first TE ADA+ titer during double-blind phase

The following descriptive listings will also be provided:

- listing of patients with TE ADA at any time during study, NAb Status will also be displayed
- listing of patients with inconclusive ADA or inconclusive NAb at any time

- listing of patients with ADA present at any time or TE hypersensitivity events or TEAEs related to injection sites.

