Note: Patients with major depressive disorder or generalized anxiety disorder, whose disease state is considered stable and expected to remain stable throughout the course of the study, in the opinion of the investigator, may be considered for inclusion if they are not on excluded medication(s).

20. Are considered by the investigator to be at significant risk for suicide.

21. Women who are pregnant or nursing.

22. Any of the following cardiovascular-related conditions are exclusionary:

- a. Prior to Visit 3 (randomization), have ECGs showing acute abnormalities of:
 - i. evidence of delayed ventricular repolarization including but not limited to a corrected QT (Bazett's QT interval [QTcB]) interval >470 msec for women and >450 for men, **and/or**
 - ii. evidence of atrioventricular (AV) depolarization of PR>220, or conduction delay of QRS>120, **and/or**

- iii. evidence of ischemia or any of the qualitative findings indicative of ST or J-point elevation, excluding those findings consistent with early repolarization (non-ischemic).
- b. History of myocardial infarction (MI), unstable angina (UA), percutaneous coronary intervention, coronary artery bypass graft, or deep vein thrombosis/pulmonary embolism within 6 months of screening, or have planned cardiovascular surgery or percutaneous coronary angioplasty.
- c. Any lifetime history of vasospastic angina or stroke, or recent history (6 months) of emergency room visit for chest pain in which an ischemic or cardiac event was not ruled out.
- d. Clinical evidence of peripheral vascular disease (e.g., Buerger's Disease) or a diagnosis of Raynaud's Phenomenon.
- e. Have any history of intracranial or carotid aneurysm, intracranial hemorrhage, or stroke.
- f. Have uncontrolled high blood pressure, characterized by systolic blood pressure >160 mmHg or diastolic blood pressure >100 mmHg on 2 or more blood pressure assessments prior to Visit 3.

23. Any of the following medical conditions are exclusionary:

- a. Have a lifetime history of seizures (except for childhood febrile seizures).
- b. Have a history or presence of any other medical illness including but not limited to any cardiovascular, hepatic, respiratory, hematological, endocrine, psychiatric or neurological disease, or any clinically significant laboratory abnormality, that in the judgment of the investigator, indicates a medical problem that would preclude study participation.

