									Phone visits (V4 and V6) are contacts between office visits to collect any spontaneously reported AE

CCI

RNA storage sample	X	X	X		X		X		Sample must be collected in a Tempus tube
PGI-I					X			X	
C-SSRS/SHSF, SHFU	X	X	X	X		X		X	To be completed at scheduled and unscheduled office visits
Recording of AEs	X	X	X	X	X	X	X	X	
Review Diary data				X		X		X	Following Informed Consent, patients are required to complete their diaries daily beginning on the day of their next cluster headache attack. Sites should review the diary compliance with the patient during office visits.
Concomitant medications	X	X	X	X	X	X	X	X	

Abbreviations: AE = adverse event; approx. = approximately; b/w = between; CGRP = calcitonin-gene related peptide; C-SSRS = Columbia-Suicide Severity Rating Scale; d = day; ECG = electrocardiogram; ePRO = electronic patient-reported outcome; ET = early termination; FSH = follicle stimulating hormone; hrs = hours; IP = investigational product; min = minute; PGI-I = Patient Global Impression of Improvement; Ph = phone; Pre-Rand. = pre-randomization; PK = pharmacokinetics; SHSF = Self-Harm Supplement Form; SHFU = Self-Harm Follow-Up Form; SP = Study Phase; V = visit; yr = year.

^a Selected tests may be obtained in the event of a treatment-emergent hepatic abnormality and may be required in follow-up with patients in consultation with the Lilly, or its designee, clinical research physician. See [Attachment 3](#) for more details regarding specific hepatic monitoring tests. If the patient has discontinued the trial and returns for hepatic follow-up, the site should use the 800 series as the visit designation.

Study Schedule, I5Q-MC-CGAL, SP IV-ET

Study Phase (SP)	SP IV		ET	Comments
Description	Post-treatment			
Interval (days) since previous office visit	60	60		
Interval allowance (days)	+/- 8	+/- 8		
Visit	8	9		
Visit Day	Day 120	Day 180	ET	
Month	4	6		
ECG		X	X	All ECGs should be collected prior to blood draws and dosing. Patients must be supine for approx. 5-10 min before ECG collection and remain supine but awake during ECG collection
Weight		X	X	
Vital signs	X	X	X	Vital signs will be taken at scheduled and unscheduled office visits and include body temperature, blood pressure, and pulse. Blood pressure and pulse will be measured in triplicate in the sitting position and should be measured prior to blood draws. Blood pressure will be assessed by utilizing a calibrated machine that will be provided to the sites.
Hematology		X	X	

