5.5.1.6. Baseline and Postbaseline Definition

Table [CGAL.5.2](#) describes the rules for determining the patient population and baseline and postbaseline observations for each study phase and type of analysis. When “last of Visit x-x” is used in the table, the last nonmissing observation obtained in the visit interval will be used.

Table CGAL.5.2. Patient Population with Baseline and Postbaseline Definitions by Study Phase and Type of Analysis

Study Phase/Analysis	Patient Population	Baseline Observation	Postbaseline Observation(s)
Study Phase III			
Continuous secondary efficacy analyses (Repeated measures)	Patients in ITT population with a baseline and at least 1 postbaseline observation	Visit 3	All Visits 4-7
TEAEs	Safety population	All Visits 1-3 before dosing	Visit 3 after dosing through Visit 7
SAEs, Discontinuations due to AEs	Safety population	NA	Visit 3 after dosing through Visit 7
C-SSRS categorical analyses	Patients in safety population with a baseline and at least one postbaseline C-SSRS assessment	Recent history: All Visits 1-3 excluding lifetime ^a All prior history: Visits 1- 3 including lifetime ^a	All Visits 3.01-7
TE abnormal laboratory values	Patients in safety population with normal laboratory values at all nonmissing baseline visits (with respect to direction being analyzed) and who have at least 1 postbaseline observation	All Visits 1-3	All Visits 3.01-7
TE immunogenicity	Patients in safety population who are evaluable for TE ADA	Visit 3	All Visits 3.01-7
TE changes in vital signs and weight, ECG parameters	Patients in safety population with a baseline and at least 1 postbaseline observation	Last nonmissing value from Visits 1-3 for BP, pulse, and ECG All Visits 1-3 for weight and temperature	Visits 3.01-7

Patient Population with Baseline and Postbaseline Definitions by Study Phase and Type of Analysis

Study Phase/Analysis	Patient Population	Baseline Observation	Postbaseline Observation(s)
Continuous safety analysis of vital signs, weight, laboratory, and ECG parameters (Box-whisker plot)	Safety population	Last non-missing value from Visits 1-3	Visits 4-7
Study Phase III and IV Combined			
TE immunogenicity	Patients in safety population who are evaluable for TE ADA	Visit 3	All Visits 3.01-9
Study Phase IV			
Post TEAEs	Posttreatment population	All Visits 1-7	All Visits 7.01-9
SAEs, Discontinuations due to AEs	Posttreatment population	NA	All Visits 7.01-9

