5.5.9.2. Continuous Safety Measures

Analyses of continuous safety data will be conducted on patients who have a baseline and at least 1 postbaseline observation for SP III.

For all the continuous safety measures (including planned laboratory measures, vital signs and weight, ECG intervals and heart rate), box-whisker plots with summary statistic tables for absolute value and change from baseline at scheduled visit and at endpoint (defined as the final postbaseline value) will be provided for SP III. The change from baseline results will be compared between treatment arms using the analysis of covariance (ANCOVA) model with treatment, pooled investigative site and baseline value in the model.

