5.8. Reports to Be Generated at Each Interim and Final Database Lock

5.8.1.1. Reports to Be Generated at Interim Database Lock

For the interim analysis, the database will be locked after all randomized patients have had the chance to complete 8 weeks of treatment in SP III. However, some patients will still be ongoing in SP IV at the time of the database lock. Data up to the data cutoff date in the locked database from all study phases will be used, and analyses specified in this SAP will be performed. However, only analyses conducted for SP III at interim analysis will be considered as the final

analyses. The analyses including data from SP IV will be rerun and updated when the completed data are available at the final database lock.

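### SAP 5.5.9.1.4 drops all of a patient's QT/QTc values because of one ECG with QRS of 120 ms or more; read literally, SP III QTc membership then depends on SP IV tracings

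*SAP*

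**What the plan says.** SAP 5.5.9.1.4 sets the exclusion: "For patients with QRS ≥ 120 milliseconds at any time during the study, the QT and QTc interval will be excluded from the analyses". It adds: "A listing of ECG data for patients with QRS ≥ 120 milliseconds at any time during the study will be provided". No reason is given for the patient-level, whole-study scope, and the ECG analysis section of the protocol (12.2.10.5) has no such exclusion.

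Other parts of the plan that bear on it:

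- **Entry.** Protocol 8.2, criterion 22a, excludes patients whose ECG before Visit 3 shows "evidence of atrioventricular (AV) depolarization of PR>220, or conduction delay of QRS>120". A QRS of exactly 120 ms is therefore eligible.
- **QRS as an outcome.** Table CGAL.5.5 counts QRS of 120 ms or more as a treatment-emergent high value, compared between arms by Fisher's exact test in SP III.
- **Phase windows.** In Table CGAL.5.2, the SP III row for "TE changes in vital signs and weight, ECG parameters" takes post-baseline data from Visits 3.01 to 7. The SP IV row takes Visits 7.01 to 9.
- **ECG schedule.** In Protocol Attachment 1, the only scheduled post-dose ECG in SP III is at Visit 7 (Day 60). The SP IV schedule has one at Visit 9 (Day 180) and one at early termination, but none at Visit 8.
- **Lock.** SAP 5.8.1.1 says that "some patients will still be ongoing in SP IV at the time of the database lock", yet treats the SP III analyses from that lock as final. Analyses that include SP IV data are rerun later.

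**The concern.** There are two separate problems.

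First, one ECG finding decides whether all of a patient's QTc values count. Because entry already screens out QRS above 120 ms, the rule acts largely on tracings taken after dosing. Membership of the QTc analysis is then partly set by a post-randomization cardiac measurement that is itself a safety outcome, and randomization does not protect a comparison selected in that way. As a hypothetical case, a man with QTcF 510 ms and QRS 98 ms at Visit 7 would leave the count above 500 ms if his Visit 9 QRS were 121 ms.

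Second, the rule looks across the whole study, while the SP III analyses are frozen before the study ends. At the lock, SP IV tracings already taken would count and later ones could not. A patient's inclusion in SP III QTc would then depend partly on how early he or she was enrolled.

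The categorical QTcF outcomes and the SP III box plots and ANCOVA for ECG intervals (SAP 5.5.9.2) are all affected. Outlier counts of this kind are usually small, so one or two patients can matter.

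**Working it through.** The plan states no figure for this rule, so there is none to reproduce.

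**Step 1: who triggers the rule.** Most triggers are post-dose, because of criterion 22a. Pre-dose triggers remain possible in three ways:
- a baseline of exactly 120 ms is eligible;
- entry uses the site's reading and analysis uses the central overread (Protocol 10.2.2.1), and the two may differ;
- SAP Appendix 1 foresees entry with QRS above 120 ms as an important deviation.

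**Step 2: what is lost.** All QT/QTc values of the patient leave the analyses, including those from ECGs with QRS below 120 ms. The ECG data stay in a listing.

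**Step 3: timing.** An SP III QTc set that requires no wide QRS at any time in the study needs every patient's Visit 9 or early-termination ECG. SAP 5.8.1.1 freezes SP III before all of those exist. The SAP revision history justifies the freeze by all patients having completed SP III. For QTc under this rule, that is not sufficient.

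**Step 4: size, on assumptions.** The documents give no QRS mean or SD, so the following are assumed. True QRS for patient i is Normal(m, SD_b²). Each ECG adds independent Normal(0, SD_w²) error. Patients enter if the baseline reading is at most 120 ms. They are excluded if the Visit 7 or the Visit 9 reading is at least 120 ms. Each row below comes from 8 million simulated patients. The count is the rate × 81 (half of the planned 162). The last column is Visit 9 only ÷ any.

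| m / SD_b / SD_w, drug shift | Any exclusion (per 81) | Wide at Visit 7 | Visit 9 only | Visit 9-only share |
|---|---|---|---|---|
| 92/8/4, none | 0.12% (0.1) | 0.06% | 0.05% | 45% |
| 90/10/5, none | 0.44% (0.4) | 0.25% | 0.19% | 44% |
| 96/10/5, none | 1.67% (1.4) | 0.96% | 0.71% | 42% |
| 100/10/5, none | 3.46% (2.8) | 2.03% | 1.43% | 41% |
| 96/10/5, +3 ms at both visits | 3.57% (2.9) | 2.15% | 1.42% | 40% |
| 96/10/5, +5 ms at both visits | 5.55% (4.5) | 3.45% | 2.10% | 38% |
| 96/10/5, +3 ms at Visit 7 only | 2.70% (2.2) | 2.15% | 0.55% | 20% |
| 96/10/5, +5 ms at Visit 7 only | 3.88% (3.1) | 3.45% | 0.43% | 11% |

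The last two rows matter because Visit 9 (Day 180) falls 180 − 30 = 150 days after the second and last dose.

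The chance that at least one of 162 patients is excluded for Visit 9 alone is 1 − (1 − q)^162, where q is the Visit 9-only rate. With no drug effect, q = 0.71% gives about 68%. Over the no-effect rows it runs from about 8% to 90%.

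**Step 5: leverage on a sparse table.** With invented counts, 6/81 versus 0/81 gives Fisher p = 0.028. Removing two of the affected patients gives 4/79 versus 0/81, p = 0.057.

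**Step 6: what an ECG-level rule recovers.** The Visit 9-only patients return to SP III. Those with a wide QRS at Visit 7 lose their only scheduled SP III post-dose QTc under either rule. In the m = 96 rows they are 0.96/1.67 = 57% of exclusions with no effect, 60% to 62% with a persistent shift, and 80% to 89% if the shift has gone by Day 180.

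**The case against.** **The phrase may be meant by phase.** SAP 5.5.9.1.4 uses almost the same words for treatment-emergent ECG abnormalities, and those are split into SP III and SP IV windows by Table CGAL.5.2 and section 5.5.9.1. The exclusion could be read in the same way. It is also arguable that a QTc analysis filtered by SP IV ECGs counts as one that includes SP IV data, and so would be rerun. Either reading may be what was intended, but neither is stated for the exclusion. A reader might infer a proven contradiction with the lock plan, or that final SP III counts will change. The documents do not go that far: they leave the scope unresolved, and the literal wording produces the dependence.

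**The signal is not hidden.** This stands. QRS of 120 ms or more is compared by arm, conduction findings and shift tables are produced without this exclusion, and every excluded patient's ECG data are listed. A reader might infer that the rule would conceal a cardiac effect. These outputs speak against that. They do not, however, restore the QTcF counts, box plots or treatment comparison.

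**Not all triggers are post-dose.** This also stands, for the reasons in Step 1. Criterion 22a is moreover framed around acute abnormalities, which leaves room for long-standing conduction delay. It would be wrong to say that the rule acts only on post-dose findings.

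**QTc is hard to interpret when QRS is wide.** Agreed. That supports dropping the wide tracing, not the patient's narrow ones.

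**The numbers are fragile.** They are. The QRS inputs are assumed, and the SAP revision history says that enrollment ended early, so 81 per arm is only a scale.

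**Conclusion.** The point holds as a minor one. The patient-level rule discards valid QTc from narrow-QRS ECGs, largely because of post-dose tracings. Its literal wording leaves SP III QTc membership open when SP III is declared final. Both statements follow from the text and need no numerical assumption.

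The size is small and uncertain. With no drug effect, about 0.1% to 3.5% of patients are excluded (0.1 to 2.8 of 81), for assumed QRS means of 90 to 100 ms, between-patient SD 8 to 10 and within-patient SD 4 to 5. Roughly 40 to 45% of these are excluded for Visit 9 alone. With a drug shift of 3 to 5 ms, exclusions rise to 2.7% to 5.5%. The Visit 9-only share is then near 40% if the shift persists to Day 180, and about 10 to 20% if it does not.

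Nothing in the documents shows that the rule would bias the QTc result in a particular direction or mask a signal.

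**What to change.** Reword the sentence in SAP 5.5.9.1.4 so that QT and QTc are excluded only from individual ECGs with QRS of 120 ms or more, applied within the phase in which the ECG was taken. Keep the listing of patients with such ECGs. The same section already excludes at ECG level for the qualitative summaries, so this fits the SAP's own practice.

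This ends the dependence on SP IV and restores narrow-QRS values. It is not a full cure. A patient whose only SP III post-dose ECG has QRS of 120 ms or more still has no SP III post-baseline QTc. Show the number of such patients by arm beside the QTc table, so that the remaining selection is visible.

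The cost is one sentence, a simpler data filter and one added line in a table. Some patients will contribute QTc at some visits and not at others.
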